### **Treatments:**

Compression therapy with either class 1 or class 2 compression stockings will be administered to 90 patients with PVD and/or CVD. The selection of the compression class was based on the CEAP class and the severity of tibial MVP abnormalities according to radiophlebography data. The researcher will select the size of the compression product according to the standard scheme after verifying the diagnosis by pelvic and lower extremity vein DUS and radionuclide assessment of venous outflow from the pelvic and lower extremity veins (radionuclide venography and SPECT).

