### **Secondary endpoint of the study**

To assess the efficacy and comfort of utilizing compression stockings of class 1 and 2 in the treatment of lower limbs venous outflow disorders and correction of lower limb muscular-venous pump dysfunction in patients with PCS in combination with subclinical and clinically manifested lower limb CVD.

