### **Study design**

This is a single-center, prospective, comparative cohort study. The duration of the study is from 1/4/2023 to 1/12/2023. The study includes 90 patients (40 patients with symptomatic PVV without CVD, 40 patients with asymptomatic PVV and symptoms of CVD, 10 patients with lower limb varicose vein disease (CVD) without PVV).

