**Exclusion criteria:**

- Menopause;
- Pregnancy;
- Postthrombotic syndrome;
- Suspicion of May-Turner syndrome;
- Ultrasound signs of nutcracker syndrome.

Before being included in the study, every patient signs a voluntary informed consent form to participate in the research.

The study enrolled 90 female patients, including 80 patients with PVV and 10 patients with CVD without PVV. All patients undergo a physician examination and receive DUS of pelvic veins and lower limbs, regardless of the presence or absence of clinical manifestations of diseases of pelvic veins and lower limbs. Then the patients are classified into three groups based on clinical and ultrasound evaluation. The first group (n=40) comprises patients with symptomatic PVV, including pelvic pain, dyspareunia, and heaviness in the hypogastrium, but without symptoms or signs of CVD. The second group (n=40) consists of women with asymptomatic PVV but with indications of CVD. The third group consists of 10 patients with varicose veins in the lower limb, without PVV or PCS symptoms. All patients undergo radionuclide venography of the lower limbs and emission computed tomography (SPECT) of the pelvic veins with *in vivo* labelled red blood cells (RBC). Quantitative indicators of the function of the lower extremity muscle-venous pump (MVP) and the pelvic venous congestion syndrome coefficient (Cpvc) are objectively assessed, using the results of radionuclide venography and single-photon emission computed tomography (SPECT). These indicators include average radiopharmaceutical transport time from regions of interest, and objectively represent blood venous flow from the veins of the lower extremities and the pelvis. Compression treatment using class 1 or 2 stockings is prescribed for patients with impaired venous outflow from the lower limbs and impaired venous evacuation function of the lower leg vein duct, depending on the class of CVD according to CEAP. Follow-up examinations, including clinical evaluations and radionuclide studies with SPECT of the pelvic veins, are performed 10 days after the initial clinical examination and radionuclide phlebography to evaluate the efficacy of the compression treatment.

Radionuclide venography with single-photon emission computed tomography (SPECT) of the pelvic veins and repeated clinical examinations are performed to evaluate the efficacy of the compression treatment 10 days after the initial clinical examination. Figure 1 displays the study's design.

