6. *Compression treatment.* Compression stockings of class 1 and 2 will be utilized as a method of compression therapy. The selection of compression class relies on the CVD classification as outlined by CEAP and the existence of impairments in the evacuation function of the lower extremity MVP in regards to the radiophlebography data of the lower limbs. The patient is instructed to wear these stockings for 10 consecutive days, 8 hours daily, following which repeated clinical and radionuclide examinations will be conducted to evaluate the efficacy of the treatment. The comfort level of the compression socks will be evaluated using a visual analog scale. This 10 cm long horizontal line assigns 1 point to each centimeter. Based on patient assessments, the following gradations of comfort will be identified: 9-10 points - complete absence of discomfort, comfortable wearing of the knitwear for 8 hours or more; 7-8 points - minor short-term mild discomfort (mild discomfort: a feeling of squeezing, sliding), which does not interfere with wearing the knitwear for 8 hours; 4-6 points - average severity of discomfort, the patient has difficulties using the stockings for 8 hours; 1-3 points - severe degree of discomfort, inability to use compression stockings.

Data from clinical examinations, ultrasound, and radionuclide studies are documented in the patient's personal medical record.

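### The protocol describes who receives compression and what sets the stocking class in three ways that are not equivalent, and none of them supports a class 1 versus class 2 efficacy claim

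*Protocol*

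**What the plan says.** Three places in the protocol describe the assignment of compression.

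- **Treatments.** Compression "will be administered to 90 patients with PVD and/or CVD". On class: "The selection of the compression class was based on the CEAP class and the severity of tibial MVP abnormalities according to radiophlebography data".
- **Study description, under Exclusion criteria.** Compression "is prescribed for patients with impaired venous outflow from the lower limbs and impaired venous evacuation function of the lower leg vein duct". Impairment therefore decides who is treated. The choice between the two stocking classes is then made "depending on the class of CVD according to CEAP".
- **Item 6, Compression treatment.** "The selection of compression class relies on the CVD classification as outlined by CEAP and the existence of impairments in the evacuation function". The function meant is that of the lower-limb pump. This item does not restrict who is treated.

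Group 1 (n=40) has symptomatic pelvic varicose veins "but without symptoms or signs of CVD". The secondary endpoint is "To assess the efficacy and comfort of utilizing compression stockings of class 1 and 2" in patients with pelvic congestion syndrome and subclinical or clinically manifest CVD. Study design states: "This is a single-center, prospective, comparative cohort study". For quantitative variables, Data processing and statistical analysis names Student's test and the Mann-Whitney U test, both unadjusted.

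**The concern.** The assignment rule is part of the intervention, so it has to read the same way wherever it is stated. Here the texts differ on two matters: whether everyone or only impaired patients receive stockings, and whether class depends on CEAP alone, on CEAP with a yes/no finding of pump impairment, or on CEAP with a graded one. Two investigators could handle the same woman differently and each be following the protocol.

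Group 1 is where this bites. One of the protocol's stated objectives is to determine indications for compression in women with pelvic varicose veins but no symptomatic CVD, and the CVD classification says least about these women.

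A second issue follows for the analysis. If results are set out by stocking class, a difference between classes will partly or wholly reflect which patients were given each class.

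**Working it through.** **1. The three texts side by side.** The protocol gives no figure to reproduce here, apart from the group sizes, which add up: 40 + 40 + 10 = 90. To test whether the texts are equivalent, take three hypothetical group 1 patients with the same CEAP class who differ only in pump function on venography.

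| Patient | Treatments | Item 6 | Study description |
|---|---|---|---|
| No impairment | treated; class may reflect no abnormality | treatment not restricted; class may reflect no impairment | not prescribed compression |
| Mild impairment | class may differ from the severe case | same class as the severe case | same class as the severe case |
| Severe impairment | class may differ from the mild case | same class as the mild case | same class as the mild case |

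No two columns agree. Treatments can separate mild from severe; the other two cannot. Item 6 can separate impaired from unimpaired patients if both are treated; the study description instead leaves the unimpaired untreated. If the study description's restriction is carried into item 6, every treated patient has impairment, and item 6 reduces to CEAP alone.

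**2. Number treated.** Treatments gives 90. The study description gives the number found to be impaired, which is not stated and can be at most 90. The denominator of the secondary endpoint therefore depends on which text is followed.

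**3. Group 1 under CEAP alone.** If clinical CVD class is the same for all 40, the split is 40/0 and no class contrast exists within the group. If some rule did split the group, the detectable standardised difference (assuming two-sided alpha 0.05 and 80% power, neither stated in the protocol) is (1.960 + 0.842) × √(1/n₁ + 1/n₂):

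- 20/20: 2.802 × √0.1000 = 0.89 SD
- 30/10: 2.802 × √0.1333 = 1.02 SD
- 35/5: 2.802 × √0.2286 = 1.34 SD

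**4. Bias in a pooled class comparison.** Assume that stocking class has no effect, that all 40 of group 1 wear one class, that a share s of group 2 (n=40) wears the other, and that group 3 is left aside. Let D be the group 1 versus group 2 difference in outcome. The first class contains 40 + 40(1 − s) patients, of whom 40(1 − s) are from group 2; the second class is all group 2. The spurious class difference is

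D × [1 − 40(1 − s) / (40 + 40(1 − s))] = D / (2 − s).

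- s = 25%: 1/1.75 = 57% of D
- s = 50%: 1/1.50 = 67% of D
- s = 75%: 1/1.25 = 80% of D
- s = 100%: 1/1.00 = 100% of D

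The shares s are assumptions; the protocol gives no expected distribution of classes.

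**5. The same problem under the other texts.** Under Treatments and item 6, class depends partly on the baseline venography, and that examination is repeated at 10 days to judge efficacy. Class is then tied to the starting value of the outcome itself.

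**The case against.** The strongest reply is that this is loose drafting. Treatments and item 6 name the same two inputs, CEAP and pump function, and differ in one word: severity or existence. The study description also mentions both and is a summary, while item 6 is the dedicated section. Part of this stands: the larger conflict is CEAP with pump function against CEAP alone. But a graded and a yes/no criterion are not interchangeable, and the difference between treating all 90 and treating only the impaired cannot be put down to summarising.

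It can also be said that confounding by severity is expected in a declared cohort and that adjustment belongs in an analysis plan. That is fair: the missing adjustment is not itself a fault here, and settling on one rule would not remove the confounding. What remains is a limit on what may be concluded.

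Several stronger readings are tempting, and the documents do not support them.

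- *The secondary endpoint cannot be interpreted.* Its text asks for no class 1 versus class 2 contrast, and examinations before treatment and at 10 days are planned.
- *Only the Treatments text could produce both classes in group 1.* If all 90 are treated, item 6 could also do so.
- *CEAP failing to split group 1 is a contradiction.* Nothing requires both classes in that group. That CEAP is constant there is also an inference: the inclusion criteria list superficial reflux, and the endpoint mentions subclinical CVD.
- *44% of patients are affected.* 40/90 is group 1's share of enrolment, not a rate of misassignment or a measure of bias.
- *No mapping to class 1 or 2 exists.* None appears in the text at hand, but the design figure is not shown and some text was removed.

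**Conclusion.** The point holds as an inconsistency in the assignment rule together with a limit on inference. The three texts are not equivalent on who is treated or on what sets the class, and they cannot all be followed. The effect is greatest in group 1 (n=40), on the natural reading that women without symptoms or signs of CVD differ little or not at all in clinical CVD class.

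No stated figure changes. The 57% to 100% range is an illustration resting on the assumed allocations above; it shows that a pooled unadjusted class comparison would be mostly a comparison of groups. Because class follows baseline severity or group under every version of the rule, and allocation is not randomised, a class 1 versus class 2 efficacy claim would not be supported. Overall change from baseline and comfort on the visual analogue scale remain interpretable.

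**What to change.** 1. Reconcile Treatments, the study description under Exclusion criteria, and item 6 into one rule, worded identically in all three places, stating who receives compression and what determines the class. Which clinical rule is right is for the sponsor; this review takes no position.
2. Report the secondary endpoint as change from baseline within stocking class and group, with the number treated in each cell.
3. Make no class 1 versus class 2 efficacy claim. If a contrast is shown, adjust it for baseline transit time, CEAP and group, and label it exploratory. Where a group wears only one class, state that no contrast can be estimated there.

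The cost is rewording in three places and a small change to the tables. The downside is a weaker claim about the stocking classes. No additional patients or examinations are needed for the reporting changes.

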## **Safety of research and treatment**

If any side effects or adverse events occur due to the administration of radiopharmaceuticals or use of compression products, they are reported and all necessary measures are taken to control these side effects and adverse reactions.

### **Follow-up**

For a period of two months following the study's conclusion, each patient will undergo monitoring in order to identify the presence of any side effects or adverse events. Furthermore, continuous assessment of the treatment's efficacy will be conducted during this period.

### **Data processing and statistical analysis**

The data of interest are analyzed using the MS Excel program to create summary tables. Statistical analysis is performed using MS Excel, Statistica 6.0, and the VassarStats online calculator (open source project). The arithmetic mean (M) and standard deviation (SD) were calculated. Qualitative variables are compared using Fisher's exact test, and quantitative variables are compared using Student's criterion or Mann-Whitney U test, as appropriate. Statistical significance was assumed at P value under 0.05.

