## **Material and methods.**

This study enrolled 90 female patients, including 40 patients with PVV and PCS, 40 patients with combined PVV and CVD, and 10 patients with CVD without pelvic vein pathology.

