### **Primary endpoint of the study**

To investigate the impact of varicose veins of the pelvis and pelvic congestion syndrome on the venous outflow of the lower limbs and the function of the muscular-venous pump of the lower limbs.

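### For contrasts with the group of 10, neither Student's pooled t-test nor Mann-Whitney holds the 0.05 level if the group spreads differ; the plan should name Welch's version of the t-test.

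*Protocol*

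**What the plan says.** The protocol's section on data processing and statistical analysis gives one rule for all quantitative variables: "quantitative variables are compared using Student's criterion or Mann-Whitney U test, as appropriate". The level follows: "Statistical significance was assumed at P value under 0.05". The section does not say whether the t-test pools the variances, does not mention Welch's version, and does not say what decides between the two tests.

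The group sizes are fixed in several places. Material and methods gives 90 women, "including 40 patients with PVV and PCS, 40 patients with combined PVV and CVD, and 10 patients with CVD without pelvic vein pathology". The text under Exclusion criteria defines them further. It puts 40 women whose PVV causes symptoms in group 1 and another 40, with silent PVV and signs of leg disease, in group 2. Of the remaining women it says: "The third group consists of 10 patients with varicose veins in the lower limb, without PVV or PCS symptoms". The Study design section states: "This is a single-center, prospective, comparative cohort study". It does not list the contrasts to be tested. The primary endpoint is stated as an aim: "To investigate the impact of varicose veins of the pelvis and pelvic congestion syndrome on the venous outflow of the lower limbs", together with the function of the muscular-venous pump.

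**The concern.** To show what PVV does to leg outflow, women with PVV must be compared with women without it. Only the third group lacks PVV, and it has 10 women. The contrasts closest to the primary aim are therefore the most unbalanced ones. Group 2 against group 3, both with chronic venous disease of the legs, is 40 vs 10.

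A pooled t-test is insensitive to unequal spread when the groups are of equal size, but not at 4:1. The pooled variance is then governed mainly by the large group, while the uncertainty of the difference comes mainly from the small one. If the 10 women vary more than the 40, the standard error is too small and PVV is declared to affect outflow too often. If they vary less, the standard error is too large and a real effect is more easily missed. The other test on the list does not remove the problem.

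**Working it through.** **Inputs.** Group sizes 40, 40 and 10, and level 0.05, from the protocol. Sidedness is not stated; two-sided is assumed. No SD is given, so the ratio r = SD(group of 10) / SD(group of 40) is an assumption and is varied. Data are simulated as normal with equal means.

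**Formula.** Set the SD in the group of 40 to 1. The true variance of the difference in means is 1/40 + r²/10. Student's test uses a variance whose expected value is [(39 + 9r²)/48] × (1/40 + 1/10).

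- r = 1: true 0.125, pooled 0.125. They agree.
- r = 2: true 0.025 + 0.4 = 0.425; pooled (75/48) × 0.125 = 0.195. The standard error used is √(0.195/0.425) = 0.68 of the true one.
- r = 0.5: true 0.025 + 0.025 = 0.050; pooled (41.25/48) × 0.125 = 0.107. The standard error used is √(0.107/0.050) = 1.46 times the true one.

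**The plan's own figure.** With equal SDs the pooled test rejects in 4.98% of simulated trials, which reproduces 0.05 within simulation error.

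**True type I error at 40 vs 10** (400,000 simulated trials for the t-tests; 200,000 for Mann-Whitney with the normal approximation):

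| r | Student, pooled | Mann-Whitney | Welch |
|---|---|---|---|
| 0.5 | 0.5% | 1.4% | 5.0% |
| 0.8 | 2.6% | 3.3% | 5.1% |
| 1 | 5.0% | 4.6% | 5.2% |
| 1.25 | 8.5% | 6.5% | 5.1% |
| 2 | 18.3% | 10.6% | 5.1% |

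Over the wider range r = 1/3 to 3, Student's test runs from 0.1% to 25.7% and Welch's stays between 4.95% and 5.18%.

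**Other contrasts.** At 40 vs 40 the pooled test stays between 5.0% and 5.3% for SD ratios from 1 to 3. At 80 vs 10 it gives 0.1% at r = 0.5 and 24% at r = 2.

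**Price of Welch when the SDs are equal, 40 vs 10** (difference in SD units, power of Student, then Welch):

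- 0.5: 28.4%, 26.5% (1.9 points lost)
- 0.8: 60.1%, 55.9% (4.2 points)
- 1.013: 80.2%, 75.8% (about 4.5 points)
- 1.2: 91.4%, 88.1% (3.3 points)

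At 40 vs 40 there is practically no loss (80.1% against 80.0% at 0.635 SD).

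**The case against.** The strongest reply is that the protocol never says the variances are pooled. Its wording leaves the choice of test to be made as the data suggest, and an analysis plan that is not shown could specify Welch's version. That is fair as far as it goes. Pooling is the ordinary meaning of Student's test, not a stated instruction, and nobody should infer that the protocol mandates it. But the protocol itself names the tests. The freedom it leaves is between two procedures, neither of which holds the level here when spreads differ. If Welch is meant, the line should say so.

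A second reply is that nothing in the protocol shows the spreads to be unequal. This also stands. All three groups have venous disease, and groups 2 and 3 both have disease of the legs, so group labels alone do not imply a large difference in the spread of leg transport time. The one hint concerns a pelvic measure: the pelvic congestion coefficient normally stays at or below 0.5 and rises with congestion. That suggests women without PVV may vary less, which is the conservative direction. A reader might infer from the 18% that false positives are the expected result. The documents do not support that: the error could go either way or be small.

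Third, the rule covers quantitative comparisons in general. A reader might infer that every comparison is compromised. The 40 vs 40 contrast is not.

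**Conclusion.** The point holds in a limited form. For contrasts with the group of 10, the 0.05 level is secured by neither named test unless the spreads are about equal. A moderate difference already matters for Student's test: 2.6% at a ratio of 0.8 and 8.5% at 1.25. At ratios of 0.5 and 2 it is about 0.5% and 18%, and an 80 vs 10 comparison is more sensitive still.

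These figures rest on normal data, a two-sided test, the pooled reading of Student's test, and SD ratios that are assumptions. They describe a vulnerability of the plan, not an error rate known to apply to this trial. Nor is the repair free: a reader might take Welch's test to cost nothing, but with a comparator of 10 and equal spreads it costs a few points of power. Behaviour with skewed transport times, or on a log scale, was not examined. The change is a cheap improvement that should be made.

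**What to change.** In the section on data processing and statistical analysis, state that the t-test for between-group comparisons of quantitative variables involving the group of 10 is Welch's unequal-variance test. Using it for 40 vs 40 as well is harmless and keeps one rule throughout. If a separate analysis plan exists, it should say the same.

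Mann-Whitney may stay on the list, but choosing it should not be taken as protection against unequal spread.

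The cost is one line of text and, at 40 vs 10, about 2 to 4.5 points of power if the spreads turn out equal. No change to the groups or to data collection is needed.

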### **Inclusion criteria:**

- Patient age group: 18-40 years;
- Presence of pelvic varicose veins according to DUS data;

- Reflux in the pelvic veins for more than 1 second before this DUS;
- Reflux in the superficial veins of the lower limbs.

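### Between-group contrasts in a non-randomised cohort are tested without adjustment for age, so any age difference between the groups enters the estimated impact of pelvic varicose veins on leg outflow

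*Protocol*

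**What the plan says.** The Study design section states: "This is a single-center, prospective, comparative cohort study". The text under Exclusion criteria explains how the groups arise: "Then the patients are classified into three groups based on clinical and ultrasound evaluation". The sizes are "40 patients with symptomatic PVV without CVD, 40 patients with asymptomatic PVV and symptoms of CVD, 10 patients with lower limb varicose vein disease". Group 1 has pelvic symptoms "but without symptoms or signs of CVD". Of group 2 the protocol says: "The second group (n=40) consists of women with asymptomatic PVV but with indications of CVD". Group 3 has leg varicose veins and no PVV.

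Age is limited by "Patient age group: 18-40 years" and by the exclusion of menopause.

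The primary endpoint section asks what impact PVV and pelvic congestion syndrome have on leg outflow and the muscular-venous pump.

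The data-processing section names the whole inferential method: "Qualitative variables are compared using Fisher's exact test" and "quantitative variables are compared using Student's criterion or Mann-Whitney U test, as appropriate", with significance at P below 0.05. The protocol mentions no covariate, regression, stratification or matching.

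**The concern.** The primary question concerns an effect and is answered by comparing groups that selected themselves through their disease. Nothing in the selection makes women with pelvic symptoms and no chronic venous disease (CVD), women with CVD and silent PVV, and women with CVD alone similar in age. If transit time or pump function varies with age, a crude test credits part of an age difference to PVV or to pelvic congestion, or lets an age difference hide a real effect.

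Age is known for every woman because eligibility depends on it, yet the stated tests do not use it. The Publication ethics section says that the results will feed methodological recommendations of the Ministry of Health, so a confounded contrast could reach practice.

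**Working it through.** The protocol states no effect size, SD, power or error-rate calculation, so there is no figure of its own to reproduce. What follows is an illustration.

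**Inputs from the protocol.** Group sizes 40, 40 and 10; significance level 0.05 (sidedness not stated, taken as two-sided); unadjusted two-sample test.

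**Inputs assumed.** Within-group correlation r between age and outcome of 0.3; age gap d of 0.5 to 1 SD; no true group effect; age the only imbalance.

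**Step 1: bias.** b = r × d in SD of the outcome.
- d = 0.5: b = 0.3 × 0.5 = 0.15
- d = 1: b = 0.3 × 1 = 0.30

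**Step 2: false-positive rate.** The t statistic follows a noncentral t distribution with n1 + n2 − 2 degrees of freedom and noncentrality b / √(1/n1 + 1/n2). The false-positive rate is the chance that it exceeds the two-sided 5% limits.

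| Contrast | √(1/n1 + 1/n2) | Noncentrality, b = 0.15 to 0.30 | False-positive rate |
|---|---|---|---|
| Group 2 v 3 (40 v 10) | 0.354 | 0.42 to 0.85 | 7.0% to 13.2% |
| Group 1 v 2 (40 v 40) | 0.224 | 0.67 to 1.34 | 10.2% to 26.3% |

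**Step 3: range over the assumed correlation.** If ages were uniform on 18 to 40, the age SD would be 22/√12 = 6.4 years. Let r run from 0.2 to 0.5.

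| Mean age gap | Bias (SD) | 40 v 10 | 40 v 40 |
|---|---|---|---|
| 3 years | 0.09 to 0.24 | 6% to 10% | 7% to 18% |
| 5 years | 0.16 to 0.39 | 7% to 19% | 11% to 41% |

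**Step 4: which contrast bears on PVV.** Groups 1 and 2 both have PVV. They differ in pelvic symptoms and in CVD at the same time. Groups 2 and 3 both have CVD and differ in PVV. For the impact of PVV itself, the 40 v 10 row is therefore the relevant one. The larger 40 v 40 figures belong to a contrast that cannot estimate it.

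**Step 5: day 10, only if groups are compared there.** Simulation at 40 v 40 with no true effect, an assumed baseline gap of 0.3 to 0.5 SD and a baseline to day-10 correlation of 0.5 to 0.7:

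| How the gap behaves | Raw day-10 values | Change from baseline | ANCOVA on baseline |
|---|---|---|---|
| Stable group difference | bias 0.30 to 0.50 SD; 26% to 60% | bias about 0; about 5% | bias 0.09 to 0.26 SD; 8% to 25% |
| Acts only through the baseline value | bias 0.15 to 0.35 SD; 11% to 34% | bias −0.09 to −0.25 SD; 7% to 20% | bias about 0; 4% to 6% |

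Raw day-10 values are biased in both cases. Neither alternative is safe in both.

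**The case against.** **The size is assumed.** Nothing in the protocol shows that the groups differ in age or that transit time depends on it, and the 18 to 40 limit with menopause excluded is already a control by design. This stands as to size. The restriction bounds an age gap, however, and does not remove it.

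**Covariates are often left to an analysis plan.** That is true, and a plan not shown here may add them. But the protocol does not leave the method open. It names unadjusted tests for quantitative variables, and that is the method as fixed.

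**Age is not the main confounder.** Groups 1 and 2 differ in pelvic symptoms and CVD together, and no age term can separate these. This stands, and it limits what the fix can achieve.

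**A stronger reading that the documents do not support.** A reader might infer that baseline differences also pass straight into the compression results at day 10, and that baseline-adjusted ANCOVA would cure this. No section says that day-10 values are compared between groups. The follow-up text and the Compression treatment section read most naturally as before and after in the same patient, where group differences in starting level do not enter. No paired test is named explicitly, but Student's criterion could include one. ANCOVA is also no clean cure: if clinically selected groups differ stably, it leaves bias of 0.09 to 0.26 SD under the assumptions above.

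**Conclusion.** The point holds for the between-group contrasts at baseline. The groups are clinically selected, the primary question is about an effect, and the only tests named are unadjusted, so an age difference would go uncorrected.

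Under the stated assumptions (correlation 0.3, age gap 0.5 to 1 SD, no true effect) the bias is 0.15 to 0.30 SD. The false-positive rate is 7% to 13% for PVV v no PVV among women with CVD, and 10% to 26% for group 1 v 2. These show what could happen; they do not estimate what will. It would be wrong to quote the 26% as the error rate for an effect of PVV, since both groups in that contrast have PVV.

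For day 10 the documents support only a conditional recommendation, not a finding of bias.

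**What to change.** In the data-processing section, make a linear model with group and age the main analysis for between-group comparisons of quantitative baseline outcomes. Leave CEAP class and rVCSS out of it, because adjusting for venous disease severity could remove part of the effect under study. Keep the Student and Mann-Whitney tests as a secondary display. State that the adjustment is partial and that group 1 v 2 cannot separate pelvic symptoms from CVD.

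If day-10 results are to be compared between groups, say so. Compare within-patient changes and not raw day-10 values, with baseline-adjusted ANCOVA as a sensitivity analysis.

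The cost is a few sentences and no new data. The model spends one degree of freedom and assumes a linear age effect, so residuals should be checked. Precision changes little. With p the share of patients in one of the two groups, the variance of the group effect is multiplied by about (1 − r²) × (1 + p(1 − p)d²). At r = 0.3 and d = 1 this is 0.91 × 1.25 = 1.14 for 40 v 40 (standard error up about 7%) and 0.91 × 1.16 = 1.06 for 40 v 10 (up about 3%).
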